- Social Phobia and Anxiety Inventory for Children (Beidel et al., 1995);
- Center for Epidemiological Studies-Depressed Mood scale (Radloff, 1977);
- Pittsburgh Sleep Quality Index (Buysse et al., 1989).
- the Youth Self-Report (Achenbach, 1991) of emotional and behavioral problems,

- DERS (Gratz & Roemer, 2004),
- quality of life KINDL-adolescent version (Ravens-Sieberer, 2000)
- the adolescent version of the Barrett Impulsiveness Scale (BIS-11), a measure of their own impulsivity (Patton, Stanford, & Barratt, 1995)

**Randomization.** After baseline, families will be randomized via a computerized algorithm (Stout et al., 1994) to groups below. Groups will be stratified by child age ( $\leq 15$  or over), sex, and parents participating (one vs. both).

**A. Referral for care.** Therapists will explain that gaming problems often co-occur with other mental health problems, and effective treatment for the latter may reduce gaming as well. Therapists will refer parents to local support groups such as Department of Mental Health and Addiction Services and National Association for Mental Illness support groups. Adolescents will be referred for appropriate services as well, e.g., depression, social anxiety, ADHD, or substance use depending on co-occurring problems.

**B. Referral plus Behavioral therapy** will consist of referral for other services plus 6 family sessions (adapted from Petry, unpublished; Appendix). In Session 1, therapists will review baseline information, refer for other services, and orient participants to treatment. They will remind parents that although they cannot prevent playing entirely, they can better understand why and when their child is playing and alter their reactions toward it, which may decrease the extent of play and problems. Therapists will describe methods to re-arrange the home to better monitor and be less conducive toward playing; this may include altering locations of or removing some (or all) gaming devices from the home. Therapists will review a tracking form and instruct parents how to and benefits of closely monitoring their child's playing. Children will be asked to keep their own log as well.

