### Data analysis

**Enhancing reproducibility.** Instruments chosen are reliable and valid, although some gaming specific instruments are new, and this study will assess their psychometric properties (see below). Careful training of evaluators will precede study initiation, and assessment interviews will be audiotaped and rated for reliability when participants agree to taping (see Human Subjects; >90% of participants agree to taping in our trials). Evaluators blind to treatment conditions will conduct assessments, and obtaining information from multiple sources (parent and child) will allow for assessment of concordance between reports (see below).

**Primary aims.** We will examine baseline (BL) indices and other services received during treatment using the Treatment Service Review, and any differences between groups that relate to outcome can be used as covariates in subsequent analyses. Analysis will be conducted on an intent-to-treat basis, using all randomly assigned subjects. We will evaluate during treatment (BL to post-treatment) and longer-term (follow-up) effects.

**Aim 1:** To evaluate the feasibility and acceptability of this intervention, the proportion assigned to the intervention who complete all 6 sessions will be examined, as will parent and child ratings of satisfaction.

**Aim 2:** To examine the effect size of the intervention on reducing game playing days and durations of play, we will analyze TLFB data collected at each assessment period, with the greater report of parent or child

used for each day. Hierarchical linear models (HLM; Gibbons et al., 1993; Raudenbush & Bryk, 2002) will compare differences between groups over time. HLM is specifically designed for repeated measures designs with missing data, allowing for intra-subject serial correlation and unequal variance and covariance structures over time by incorporating available trend data for each individual with information on the group from which the subject is drawn. Maximum likelihood estimation enables analyses to be performed for the full trial without having to drop subjects with incomplete data, and both continuous and dichotomous variables can be analyzed. The model will include factors representing group, time, and their interaction, along with any important covariates.

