We will also compare proportions of subjects by group who are no longer gaming problematically, i.e., child reports no current DSM-5 IGD criteria and/or <5 criteria, and parent confirms no more problems for the most conservative approach. Logistic regressions will include important demographics and baseline indices of distress and severity of problems in Step 1. Step 2 will add treatment to determine if it adds unique variance in predicting outcomes after controlling for baseline indices.

**Power analyses.** This pilot is designed to assess feasibility, acceptability, and effect sizes. Thirty subjects per group are sufficient to address the former, to estimate effect sizes, and to detect moderately large differences of Cohen's (1988)  $d = 0.65$  with Type I error rate  $\alpha = .05$ , Type II error rate  $\beta = .20$ , and power  $[1 - \beta] = .80$ . If medium or larger effect sizes are noted, a larger randomized trial will be proposed to assess long-term efficacy.

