## 2. ADEQUACY OF PROTECTION AGAINST RISKS

### a. Recruitment and Informed Consent.

Informed Consent: A trained research staff member (Bachelors level or above), under supervision of the PI, will obtain informed consent. All potential subjects will receive an explanation of this study protocol, its potential risks and benefits, and alternative treatment available. Following resolution of any questions, parents/guardians and adult children (i.e., age 18) who agree to participate will be asked to sign the study

consent form and HIPAA document. A signed copy of the consent and HIPAA form will be given to each participant. Assent will be obtained from children under the age of 18, and both child and parent must agree to participate prior to collection of study data or randomization to a condition. As noted above, individuals who choose not to participate or who are deemed ineligible will be referred for other services as indicated.

An audiotaping section within the consent form will be utilized for recording of interactions between research staff and study patients, including baseline and follow-up interviews and therapy sessions. These audiofiles are utilized only for quality control procedures, to rate staff according to set standards in interview and treatment administration. Patients may participate in the study even if they do not choose to allow audiotaping (in our prior and ongoing studies, less than 5% of patients refuse audiotaping, and in this case both child and parent must agree or taping will not occur). The audiotaping consent section will explain that the purpose is to rate the staff member's interviewing and treatment administration skills.

b. Protection Against Risks. The following will protect against potential risks:

- i. Random group assignment is used, and about half of families will be assigned to the referral alone condition and half to the referral plus brief family behavioral therapy condition. These proportions will be outlined in the informed consent form, and patients will be made aware that they have about a 50% chance of being assigned to the family behavioral therapy condition. Patients may voluntarily end study participation if they are dissatisfied with their assignment.
- ii. The interviews and sample collections are brief, patients may skip questions or take a break if uncomfortable, and the particular instruments chosen are intended to minimize discomfort.

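### The three stratification factors are not prespecified in any model, and the stated covariate rule selects on observed group differences and can admit services received after randomisation

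*Combined protocol and SAP*

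**What the plan says.** Under Approach, Randomization, "families will be randomized via a computerized algorithm" after baseline, and "Groups will be stratified by child age" (15 or under, or over), sex, and parents participating (one versus both). No block size or balancing rule is given.

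The Data analysis section opens covariate adjustment in three places:

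- Primary aims: the stated rule is that "any differences between groups that relate to outcome can be used as covariates in subsequent analyses". What it screens is not only the baseline measures but also "other services received during treatment using the Treatment Service Review".
- Aim 2, gaming days and durations: "The model will include factors representing group, time, and their interaction, along with any important covariates". What counts as important is not defined.
- Remission of IGD: "Logistic regressions will include important demographics and baseline indices of distress and severity of problems in Step 1".

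Item 10 of the Detailed Data and Safety Monitoring Plan repeats all three. The exclusion criteria under Human Subjects likewise allow analyses to control for mental health services that differ between groups and relate to outcome. None of these places names the stratification factors as model terms.

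**The concern.** When allocation is balanced on a factor, the analysis should reflect it. Otherwise the factor's variance stays in the error term although the design has removed it from the comparison. A rule that looks for observed group differences works against this, because the balanced factors are the ones it will not find.

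The same rule has two further problems. It sets no threshold, is optional, and is applied to a large set of baseline scales after outcomes are known, so the effect estimate depends on later choices. It also covers services received during treatment, which assignment can affect.

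The estimate matters because this pilot's main product is an effect size. Under Specific aims and Power analyses, a medium or larger effect leads to a proposal for a larger trial. Under Exploratory aims, mediators are carried forward only if a main effect of treatment is seen.

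**Working it through.** **Inputs from the documents.** 30 per group, d = 0.65, alpha .05, power .80 (Power analyses: "Thirty subjects per group are sufficient to address the former, to estimate effect sizes, and to detect moderately large differences"). Allocation is about 1:1 ("about half of families will be assigned to the referral alone condition"). Three two-level factors give 2 × 2 × 2 = 8 cells, or 60/8 = 7.5 families per cell on average.

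**Assumptions, because the documents give no figure.** The factors explain a share R² of outcome variance between 0 and 0.30; factor prevalences are 50%, 80% and 40%; blocks of 2 are used within cells; data are complete; SD = 1.

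**The plan's own figure.** The noncentral t gives power 0.800 at one-sided .05, which reproduces the stated .80, and 0.697 at two-sided .05. Sidedness is not stated. The tests below are two-sided, and the simulated unadjusted power at R² = 0 (0.695) agrees with 0.697.

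**1. Does the rule find the factors?** Selecting on an observed group difference at p < .05 picked a stratification factor in 0% of simulated trials.

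**2. Omitting the factors from a linear post-treatment model** (5,000 trials per setting, true d = 0.65; null rejection from matching runs with d = 0):

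| R² | Mean effect without / with | Model SE without / with | Empirical SE without | Power without / with | Null rejection without / with |
|---|---|---|---|---|---|
| 0 | 0.648 / 0.647 | 0.257 / 0.258 | 0.256 | 0.695 / 0.693 | 0.047 / 0.047 |
| 0.10 | 0.649 / 0.649 | 0.258 / 0.245 | 0.2435 | 0.704 / 0.740 | 0.043 / 0.054 |
| 0.30 | 0.652 / 0.653 | 0.258 / 0.216 | 0.2235 | 0.718 / 0.835 | 0.021 / 0.050 |

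The Monte Carlo SE of the mean effect is about 0.003, so there is no bias. The SE overstatement is model SE over empirical SE: 0.2580/0.2435 = 1.06 and 0.2583/0.2235 = 1.16. The null runs give 0.2572/0.2492 = 1.03 and 0.2568/0.2191 = 1.17. Under perfect balance, 1/√(1 − R²) gives 1.05 and 1.20.

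**3. The planned group-by-time contrast**, in change-score form (6,000 trials, within-family correlation 0.5 given the factors, R² = 0.30). If the factors shift all visits equally they cancel, and the model SE is 0.215 without and 0.216 with them. If factor effects halve over time, the SE is 0.226 versus 0.216 and power 0.814 versus 0.834.

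**4. The logistic remission model.** Omitting three factors with odds ratios of 1.5, 2 or 3 each pulls the conditional log odds ratio toward zero by about 2%, 6% or 14% (treatment odds ratio 2 to 4). This is non-collapsibility; the marginal odds ratio is still validly estimated.

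**5. The difference-based rule.** Further assumptions: baseline correlation 0.5, 20 candidate indices of which 5 are weakly prognostic, both screens at p < 0.10, true d = 0.65.

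- Outcome relation tested with arms pooled: mean estimate 0.620 to 0.625, against 0.650 to 0.653 with baseline only (4,000 trials per setting). A second set of runs (2,000 trials) gave 0.617 to 0.629 against 0.643 to 0.656. The shrinkage is about 0.03, and 0.03/0.65 is about 5%.
- Outcome relation tested with group and baseline in the screen: 0.642 to 0.652 against 0.641 to 0.651, so no shrinkage.

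**6. Services during treatment.** Both arms are referred for care and one also has six family sessions, so uptake can respond to assignment and to early change in gaming. Conditioning on it can remove part of the effect or create a spurious one. The documents give no expected uptake, so no size can be attached.

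**The case against.** A reader might infer that the plan leaves the stratification factors out. The text does not say so. The linear models may take any important covariates and the logistic model takes important demographics, with no screen on group differences. Child age and sex are collected as basic demographics and could enter by either route, so the gap is one of prespecification.

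A reader might also infer that omission biases the gaming effect toward zero. The simulated means of 0.648 to 0.652 rule that out for the linear outcomes. Shrinkage comes from the covariate rule, and only under a pooled screen; the plan does not say which screen is meant.

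A third tempting reading is that the Aim 2 standard error as planned is too large. For the group-by-time term this holds only if factor effects change over time. If they are constant, or if R² is zero, there is nothing to gain.

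Finally, the decision on a larger trial rests on a point estimate, which an inflated standard error does not move, and the test errs on the conservative side. All of this stands and limits the size of the point. None of it supports leaving the factors unnamed, keeping an open-ended selection rule, or admitting a post-randomisation variable.

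**Conclusion.** The point holds as a modest prespecification defect. The factors used to balance allocation are not named in any model, and the one explicit selection rule almost never brings them in.

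If they are prognostic for post-baseline gaming, omission costs precision: about 6% to 16% on the standard error at an assumed R² of 0.10 to 0.30 in a post-treatment linear model. The cost is little or nothing for a group-by-time contrast with constant factor effects. Background and significance links male sex and younger age to gaming problems, which makes prognostic value plausible, but that concerns prevalence and not change within a sample that already meets IGD criteria.

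The larger weakness is the rule itself. It leaves the effect size open to choices made after outcomes are seen, worth about 0.03 at d = 0.65 under one reading and nothing under the other. It also allows adjustment for services received during treatment, where bias could go either way by an amount the documents do not let one calculate.

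**What to change.** 1. Include child age group, sex, and one versus both parents as main effects in every Aim 2 and secondary model, including Step 1 of the logistic remission model.
2. Preferably fit them in a baseline-adjusted model of the post-baseline visits. If the group-by-time form is kept, factor-by-visit terms are needed, since main effects alone leave that contrast unchanged. With the TLFB at three visits this is about nine terms: three main effects and 3 × 2 interactions.
3. Delete the rule based on observed group differences in Data analysis, in item 10 of the monitoring plan, and in the matching sentence under the exclusion criteria. Fix any other baseline covariates before outcomes are seen by arm.
4. Report services received during treatment descriptively or in a sensitivity analysis, not as a covariate in the main model.

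The cost is wording and a few degrees of freedom with main effects only. Few girls are expected, so cells involving them will be sparse. That favours main effects over the eight-cell classification and counts against the nine-term version.

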### Design considerations:

**Why this control condition?** We considered other control conditions but elected this one because it allows for evaluation of follow-up effects (unlike waitlist conditions), controls for some expectancy effects (unlike no treatment controls), and increases ability to ascertain benefits of the behavioral family therapy if they exist. A therapist attention control condition is premature in Stage 1 research (Rounsaville et al., 2000), but represents an important next step if we note benefits in this pilot trial.

**Why not focus on abstinence?** Abstinence from gaming will be encouraged for youth who are willing to consider a short- or long-term (or indefinite) goal of no game playing. Although we expect that many parents will desire that their child refrain entirely from playing, most children probably will not share this goal. To avoid alienating youth in these situations, therapists will review "normal" play (Gentile, 2009) and negotiate reasonable limits between parents and youth using recommended guidelines (Council on Communication Media, 2013), which may include an initial period of no gaming. Therapists will also encourage parents and youth to re-arrange the home environment to be less conducive toward gaming (e.g., removing gaming equipment from bedrooms) and to better identify and monitor play (e.g., by setting timers or parental controls) especially for devices that can be used for purposes beyond gaming (i.e., computers, smartphones).

**Why this duration?** A 6-week intervention allows for coverage of topics thought important for altering gaming behavior (Council on Communication Media, 2013). It is long enough to demonstrate change if it is efficacious and but not so long that topics will become redundant. It is also within the range of other brief family-based therapies (e.g., Coatsworth et al., 2001), and an even shorter 3-week (5 session) family intervention has shown promise in decreasing gaming (Han et al., 2012). Given the treatment's emphasis on developing parenting skills, the 6-week protocol allows time between sessions for parents to practice new skills at home and problem solve barriers to implementation. If this IGD treatment is efficacious in reducing gaming problems, it is likely that best practices will be to integrate it alongside other evidence-based treatments to address co-occurring substance use and mental health disorders. However, the purpose of the current study is to evaluate the feasibility, acceptability, and preliminary effect size for this IGD approach. If parents or children recommend more or fewer sessions in the therapy satisfaction questionnaire, subsequent studies can alter the duration.

### Data analysis

**Enhancing reproducibility.** Instruments chosen are reliable and valid, although some gaming specific instruments are new, and this study will assess their psychometric properties (see below). Careful training of evaluators will precede study initiation, and assessment interviews will be audiotaped and rated for reliability when participants agree to taping (see Human Subjects; >90% of participants agree to taping in our trials). Evaluators blind to treatment conditions will conduct assessments, and obtaining information from multiple sources (parent and child) will allow for assessment of concordance between reports (see below).

**Primary aims.** We will examine baseline (BL) indices and other services received during treatment using the Treatment Service Review, and any differences between groups that relate to outcome can be used as covariates in subsequent analyses. Analysis will be conducted on an intent-to-treat basis, using all randomly assigned subjects. We will evaluate during treatment (BL to post-treatment) and longer-term (follow-up) effects.

**Aim 1:** To evaluate the feasibility and acceptability of this intervention, the proportion assigned to the intervention who complete all 6 sessions will be examined, as will parent and child ratings of satisfaction.

**Aim 2:** To examine the effect size of the intervention on reducing game playing days and durations of play, we will analyze TLFB data collected at each assessment period, with the greater report of parent or child

used for each day. Hierarchical linear models (HLM; Gibbons et al., 1993; Raudenbush & Bryk, 2002) will compare differences between groups over time. HLM is specifically designed for repeated measures designs with missing data, allowing for intra-subject serial correlation and unequal variance and covariance structures over time by incorporating available trend data for each individual with information on the group from which the subject is drawn. Maximum likelihood estimation enables analyses to be performed for the full trial without having to drop subjects with incomplete data, and both continuous and dichotomous variables can be analyzed. The model will include factors representing group, time, and their interaction, along with any important covariates.

We will also compare proportions of subjects by group who are no longer gaming problematically, i.e., child reports no current DSM-5 IGD criteria and/or <5 criteria, and parent confirms no more problems for the most conservative approach. Logistic regressions will include important demographics and baseline indices of distress and severity of problems in Step 1. Step 2 will add treatment to determine if it adds unique variance in predicting outcomes after controlling for baseline indices.

**Power analyses.** This pilot is designed to assess feasibility, acceptability, and effect sizes. Thirty subjects per group are sufficient to address the former, to estimate effect sizes, and to detect moderately large differences of Cohen's (1988)  $d = 0.65$  with Type I error rate  $\alpha = .05$ , Type II error rate  $\beta = .20$ , and power  $[1 - \beta] = .80$ . If medium or larger effect sizes are noted, a larger randomized trial will be proposed to assess long-term efficacy.

**Exploratory aims** are to evaluate potential mechanisms of actions of the intervention including: changes in number and location of gaming devices in the home, frequency of monitoring child's game playing (via self reports in both groups, and confirmed by completed logs in Group B), child's participation in alternate activities (ACC), and parental rewarding of child behaviors and family communications (PSSS, BFAM scores). Following recommendations of Morgenstern and Longabaugh (2000) for assessing mediation, Model 1 examines whether the treatments engender differential outcomes on gaming indices (i.e., Aim 2 above). Model 2 will test if potential mediators change differentially over time by condition. For these analyses, a composite indicator for each construct will be utilized (e.g., summary scores of number/location of gaming devices, monitoring frequencies, ACC, PSS and BFAM scores). Model 3 will examine partial correlations between post-treatment scores on these indices and gaming outcomes, after controlling for baseline scores. If these three models show significant effects, the final model will assess associations between these variables and gaming outcomes. Step 1 of this model will include baseline scores of the potential mediator(s). In step 2, treatment group will be entered, and in step 3, post-treatment scores of the mediator(s) will be included, and resulting predictive power of treatment condition examined. If treatment is no longer significant and the post-treatment mediation term is significant, criteria for full mediation are met. Although we do not expect to find full mediation with this sample size, potential mediators with medium or higher effect sizes in Models 2-3 will be considered for future evaluation and inclusion in this intervention, if main effects of treatment are noted (Aim 2).

We will also assess effect sizes on secondary outcomes, e.g., substance use, psychosocial functioning and symptoms, sleep, and quality of life. HLM, outlined above, will compare groups over time on these indices.

Finally, we will evaluate the psychometric properties of a semi-structured diagnostic interview based on the DSM-5 IGD criteria as well as the parent version of the VGDS. Briefly, internal reliabilities of symptoms and diagnostic criteria will be calculated using Cronbach's alpha. Parent and child reports on self-report and interviews will be compared using Shrout and Fleiss intraclass correlations for continuous variables and Kappa's for diagnostic assessments, with respect to endorsement of specific criteria and diagnosis. For both parent and child versions, we will also examine correlations with TLFB gaming behavior and other indices as we did previously (Rehbein et al., 2015) to determine convergent validity. Thus, this project allows for initial psychometric evaluation of a parent report measure and a structured clinical interview for IGD in youth.

**Future directions.** This study will inform future research and treatment for IGD. In terms of assessment and diagnosis, psychometrically robust assessment tools are critically needed for research in epidemiological and clinical samples, and this study is a step toward developing and validating such tools.

In terms of treatment, if the intervention is feasible and acceptable and leads to changes in gaming beyond that of the control condition, we will propose a larger scale, longer-term study. We can modify the intervention based on experiences by removing unhelpful sessions, and adding to those that appear to lead to clinically important changes and that show promise for mediating changes in gaming. Even in the absence of

treatment-specific effects, these results will provide valuable information about how gaming and psychosocial functioning change over time. Given increasing scientific, clinical, and public interest in this condition, this study is timely and critical for addressing diagnostic and clinical concerns related to this new “addictive disorder.”

